## APPENDIX C: INTERNATIONAL PROGNOSTIC SCORING SYSTEM FOR PRIMARY MYELOFIBROSIS

The following table determines risk level using the International Prognostic Scoring System (IPSS) for PMF (primary myelofibrosis).

Risk Level	IPSS PMF Score
Low risk	0
Intermediate risk 1	1
Intermediate risk 2	2
High risk	$\geq 3$

Factors identified as predictors of shortened survival were:

- age  $>65$  years,
- presence of constitutional symptoms,
- hemoglobin  $<10$  g/dL,
- leukocyte count  $>25 \times 10^9/L$ , and
- circulating blast cells  $\geq 1\%$ .

Source: Cervantes F, Dupriez B, Pereira A, et al. New prognostic scoring system for primary myelofibrosis based on a study of the International Working Group for Myelofibrosis Research and Treatment. *Blood* 2009;113(13):2895-2901.

## APPENDIX D: EASTERN COOPERTIVE ONCOLOGY GROUP (ECOG) PERFORMANCE STATUS

Grade	Status
0	Fully active, able to carry on all pre-disease performance without restriction
1	Restricted in physically strenuous activity but ambulatory and able to carry out work of a light or sedentary nature, eg, light house work, office work
2	Ambulatory and capable of all self-care but unable to carry out any work activities. Up and about more than 50% of waking hours
3	Capable of only limited self-care, confined to bed or chair more than 50% of waking hours
4	Completely disabled. Cannot carry on any self-care. Totally confined to bed or chair
5	Dead

## APPENDIX E: PROHIBITED AND CAUTIONED MEDICATIONS – SPECIFIC CYTOCHROME P450 SUBSTRATES AND INHIBITORS/INDUCERS

The tables below list many of the medications that are prohibited or cautioned. See the website for additional medications that may not be listed. To view this website, hit CTRL+Click when your cursor is on top of this link: (<http://medicine.iupui.edu/clinpharm/ddis/table.asp>).

CYP1A2 and CYP3A4 Substrates (Drugs Substantially Metabolized by CYP1A2 or CYP3A4) Use of these drugs is prohibited		
CYP1A2 Substrates		
amitriptyline	ondansetron	
excessive caffeine	phenacetin	
clomipramine	propranolol	
clozapine	riluzole	
cyclobenzaprine	ropivacaine	
duloxetine	tacrine	
estradiol	theophylline	
fluvoxamine	tizanidine	
haloperidol	triamterene	
imipramine N-DeMe	verapamil	
mexiletine	warfarin	
naproxen	zileuton	
olanzapine	zolmitriptan	
CYP3A4 Substrates		
Macrolide antibiotics including clarithromycin, erythromycin and telithromycin (not azithromycin)		
Benzodiazapines including alprazolam, diazepam, midazolam, and triazolam		
Immune modulators including cyclosporine and tacrolimus		
Antihistamines including astemizole, and chlorpheniramine.		
Calcium channel blockers including amlodipine, diltiazem, felodipine, lercanidipine, nifedipine, nisoldipine, nitrendipine, verapamil		
HMG CoA reductase inhibitors (Statins) including atorvastatin, cerivastatin, lovastatin, simvastatin (not pravastatin and rosuvastatin)		
Steroid 6beta-OH including estradiol, hydrocortisone, progesterone, and testosterone		
Miscellaneous:		
alfentanil	eplerenone	quinidine
aprepitant	fentanyl	quinine
ariPIPrazole	finasteride	risperidone
buspirone	haloperidol	salmeterol
cafergot	LAAM	sildenafil
excessive caffeine	lidocaine	sirolimus
cilostazol	methadone	tamoxifen
cocaine	nateglinide	trazodone
codeine N-demethylation	ondansetron	zaleplon
dexamethasone	pimozide	ziprasidone
dextromethorphan	propranolol	zolpidem
domperidone	quetiapine	

CYP3A4 STRONG Inhibitors and Inducers Use of these drugs is prohibited	
CYP3A4 Inhibitors clarithromycin itraconazole ketoconazole nefazodone telithromycin	CYP3A4 Inducers rifampin St. John's Wort
CYP3A4 MODERATE Inhibitors and Inducers Use of these drugs is discouraged (alternative therapies should be considered) but does not disqualify patient participation in the study.	
CYP3A4 Inhibitors aprepitant diltiazem erythromycin fluconazole grapefruit juice verapamil	CYP3A4 Inducers carbamazepine phenobarbital phenytoin pioglitazone rifabutin troglitazone

## APPENDIX F: NEW YORK HEART ASSOCIATION (NYHA) CLASSIFICATION OF HEART FAILURE

Class	Patient Symptoms
Class I (Mild)	No limitation of physical activity. Ordinary physical activity does not cause undue fatigue, palpitation, or dyspnea (shortness of breath).
Class II (Mild)	Slight limitation of physical activity. Comfortable at rest, but ordinary physical activity results in fatigue, palpitation, or dyspnea.
Class III (Moderate)	Marked limitation of physical activity. Comfortable at rest, but less than ordinary activity causes fatigue, palpitation, or dyspnea.
Class IV (Severe)	Unable to carry out any physical activity without discomfort. Symptoms of cardiac insufficiency at rest. If any physical activity is undertaken, discomfort is increased.

Source: <http://www.merckmanuals.com/professional/sec07/ch074/ch074a.html#CEGDEIFG>

## APPENDIX G: CLINICAL LABORATORY (SAFETY) TESTS

Hematology:	erythrocytes mean corpuscular volume (MCV) mean corpuscular hemoglobin (MCH) neutrophils eosinophils basophils lymphocytes monocytes platelets leukocytes hemoglobin hematocrit	Urinalysis:	pH protein glucose ketone bilirubin blood nitrite
Clinical chemistry:	blood urea nitrogen (BUN) lactate dehydrogenase creatinine uric acid total protein albumin glucose total bilirubin magnesium amylase (first 2 cycles only) lipase (first 2 cycles only)	Liver enzymes:	alkalinephosphatase aspartateaminotransferase (AST) alanineaminotransferase (ALT)
Electrolytes:	chloride sodium potassium		
Pregnancy test:	Serum or urine, in women with childbearing potential		

## **APPENDIX H: NATIONAL CANCER INSTITUTE COMMON TOXICITY CRITERIA FOR ADVERSE EVENTS**

See the following website for NCI CTEP CTCAE version 4.0 (28 May 2009). To view this website, hit CTRL+Click when your cursor is on top of this link:

[http://ctep.cancer.gov/protocolDevelopment/electronic\\_applications/ctc.htm](http://ctep.cancer.gov/protocolDevelopment/electronic_applications/ctc.htm)

**APPENDIX I: INTERNATIONAL WORKING GROUP  
CONSENSUS CRITERIA FOR TREATMENT RESPONSE IN  
MYELOFIBROSIS WITH MYELOID METAPLASIA**

1. Complete remission (CR)	(1) Complete resolution of disease-related symptoms and signs including palpable hepatosplenomegaly.
	(2) Peripheral blood count remission defined as hemoglobin level at least 110 g/L, platelet count at least $100 \times 10^9/L$ , and absolute neutrophil count at least $1.0 \times 10^9/L$ . In addition, all 3 blood counts should be no higher than the upper normal limit.
	(3) Normal leukocyte differential including disappearance of nucleated red blood cells, blasts, and immature myeloid cells in the peripheral smear, in the absence of splenectomy.*
	(4) Bone marrow histologic remission defined as the presence of age-adjusted normocellularity, no more than 5% myeloblasts, and an osteomyelofibrosis grade no higher than 1.†
2. Partial remission (PR)	Requires all of the above criteria for CR except the requirement for bone marrow histologic remission. However, a repeat bone marrow biopsy is required in the assessment of PR and may or may not show favorable changes that do not however fulfill criteria for CR.
3. Clinical improvement (CI)	
Requires one of the following in the absence of both disease progression (as outlined below) and CR/PR assignment (CI response is validated only if it lasts for no fewer than 8 weeks)
 
(1) A minimum 2 -g/L increase in hemoglobin level or becoming transfusion independent (applicable only for patients with baseline hemoglobin level of less than 100 g/L).‡
 
(2) Either a minimum 50% reduction in palpable splenomegaly of a spleen that is at least 10 cm at baseline or a spleen that is palpable at more than 5 cm at baseline becomes not palpable.§
 
(3) A minimum 100% increase in platelet count and an absolute platelet count of at least <math>50,000 \times 10^9/L</math> (applicable only for patients with baseline platelet count below <math>50 \times 10^9/L</math>).
 
(4) A minimum 100% increase in ANC and an ANC of at least <math>0.5 \times 10^9/L</math> (applicable only for patients with baseline absolute neutrophil count below <math>1 \times 10^9/L</math>).

4. Progressive disease (PD)	Requires one of the following: 
	(1) Progressive splenomegaly that is defined by the appearance of a previously absent splenomegaly that is palpable at greater than 5 cm below the left costal margin or a minimum 100% increase in palpable distance for baseline splenomegaly of 5-10 cm or a minimum 50% increase in palpable distance for baseline splenomegaly of greater than 10 cm.
	(2) Leukemic transformation confirmed by a bone marrow blast count of at least 20%.
	(3) An increase in peripheral blood blast percentage of at least 20% that lasts for at least 8 weeks.
5. Stable disease (SD)	None of the above.
6. Relapse	Loss of CR, PR, or CI. In other words, a patient with CR or PR is considered to have undergone relapse when he or she no longer fulfills the criteria for even CI. However, changes from either CR to PR or CR/PR to CI should be documented and reported.

* Because of subjectivity in peripheral blood smear interpretation, CR does not require absence of morphologic abnormalities of red cells, platelets, and neutrophils.
 
† In patients with CR, a complete cytogenetic response is defined as failure to detect a cytogenetic abnormality in cases with a pre-existing abnormality. A partial cytogenetic response is defined as 50% or greater reduction in abnormal metaphases. In both cases, at least 20 bone marrow- or peripheral blood-derived metaphases should be analyzed. A major molecular response is defined as the absence of a specific disease-associated mutation in peripheral blood granulocytes of previously positive cases. In the absence of a cytogenetic/molecular marker, monitoring for treatment-induced inhibition of endogenous myeloid colony formation is encouraged. Finally, baseline and posttreatment bone marrow slides are to be stained at the same time and interpreted at one sitting by a central review process.
 
‡ Transfusion dependency is defined by a history of at least 2 units of red blood cell transfusions in the last month for a hemoglobin level of less than 85 g/L that was not associated with clinically overt bleeding. Similarly, during protocol therapy, transfusions for a hemoglobin level of 85 g/L or more is discouraged unless it is clinically indicated.
 
§ In splenectomized patients, palpable hepatomegaly is substituted with the same measurements.
 
   It is acknowledged that worsening cytopenia might represent progressive disease, but its inclusion as a formal criterion was avoided because of the difficulty distinguishing disease-associated from drug-induced myelosuppression. However, a decrease in hemoglobin level of 20 g/L or more, a 100% increase in transfusion requirement, and new development of transfusion dependency, each lasting for more than 3 months after the discontinuation of protocol therapy, can be considered disease progression.
	

ANC = absolute neutrophil count; CR = complete remission; CI = clinical improvement; PD = progressive disease; PR = partial response; SD = stable disease.
	

Source: Tefferi A, Barosi G, Mesa R, et al. International Working Group (IWG) consensus criteria for treatment response in myelofibrosis with myeloid metaplasia, for the IWG for Myelofibrosis Research and Treatment (IWG-MRT). *Blood*. 2006;108:1497-1503.

## APPENDIX J: MYELOFIBROSIS SYMPTOM ASSESSMENT FORM

The MF SAF is described in

**APPENDIX K: REVISED RESPONSE CRITERIA FOR  
MYELOFIBROSIS: INTERNATIONAL WORKING GROUP-  
MYELOPROLIFERATIVE NEOPLASMS RESEARCH AND  
TREATMENT (IWG-MRT) AND EUROPEAN LEUKEMIANET  
(ELN) CONSENSUS REPORT**

Response categories	Required criteria (for all response categories, benefit must last for $\geq 12$ wk to qualify as a response)
Complete Response (CR)	
Bone marrow: * Age-adjusted normocellularity; <math><5\%</math> blasts; <math>\leq</math>grade 1 MF† and
 
Peripheral blood: Hemoglobin <math>\geq 100</math> g/L and <math><</math>UNL; neutrophil count <math>\geq 1 \times 10^9/L</math> and <math><</math>UNL;
 
Platelet count <math>\geq 100 \times 10^9/L</math> and <math><</math>UNL; <math><2\%</math> immature myeloid cells‡ and
 
Clinical: Resolution of disease symptoms; spleen and liver not palpable; no evidence of EMH

Partial Response (PR)	
Peripheral blood: Hemoglobin <math>\geq 100</math> g/L and <math><</math>UNL; neutrophil count <math>\geq 1 \times 10^9/L</math> and <math><</math>UNL; platelet count <math>\geq 100 \times 10^9/L</math> and
 
<math><</math>UNL; <math><2\%</math> immature myeloid cells‡ and
 
Clinical: Resolution of disease symptoms; spleen and liver not palpable; no evidence of EMH or
 
Bone marrow: * Age-adjusted normocellularity; <math><5\%</math> blasts; <math>\leq</math>grade 1 MF†, and peripheral blood: Hemoglobin <math>\geq 85</math> but <math><100</math> g/L
 
and <math><</math>UNL; neutrophil count <math>\geq 1 \times 10^9/L</math> and <math><</math>UNL; platelet count <math>\geq 50</math>, but <math><100 \times 10^9/L</math> and <math><</math>UNL; <math><2\%</math> immature myeloid cells‡ and
 
Clinical: Resolution of disease symptoms; spleen and liver not palpable; no evidence of EMH

Clinical improvement (CI)	The achievement of anemia, spleen or symptoms response without progressive disease or increase in severity of anemia, thrombocytopenia, or neutropenia§
Anemia response	
Transfusion-independent patients: a <math>\geq 20</math> g/L increase in hemoglobin level  
 
Transfusion-dependent patients: becoming transfusion-independent{

Spleen response#	A baseline splenomegaly that is palpable at 5-10 cm, below the LCM, becomes not palpable   or
	A baseline splenomegaly that is palpable at $>10$ cm, below the LCM, decreases by $\geq 50\%**$
	A baseline splenomegaly that is palpable at $<5$ cm, below the LCM, is not eligible for spleen response
	A spleen response requires confirmation by MRI or computed tomography showing $\geq 35\%$ spleen volume reduction
Symptoms response	A $\geq 50\%$ reduction in the MPN-SAF TSS††

Progressive disease ‡‡	Appearance of a new splenomegaly that is palpable at least 5 cm below the LCM or
	A $\geq 100\%$ increase in palpable distance, below LCM, for baseline splenomegaly of 5-10 cm or
	A 50% increase in palpable distance, below LCM, for baseline splenomegaly of $>10$ cm or
	Leukemic transformation confirmed by a bone marrow blast count of $>20\%$ or A peripheral blood blast content of $\geq 20\%$ associated with an absolute blast count of $\geq 1 \times 10^9/L$ that lasts for at least 2 weeks
Stable disease	Belonging to none of the above listed response categories
Relapse	No longer meeting criteria for at least CI after achieving CR, PR, or CI, or
	Loss of anemia response persisting for at least 1 month or
	Loss of spleen response persisting for at least 1 month
Recommendations for assessing treatment-induced cytogenetic and molecular changes	
Cytogenetic remission	At least 10 metaphases must be analyzed for cytogenetic response evaluation and
	requires confirmation by repeat testing within 6 months window
	CR: eradication of a preexisting abnormality
	PR: $\geq 50\%$ reduction in abnormal metaphases (partial response applies only to patients with at least ten abnormal metaphases at baseline)
Molecular remission	Molecular response evaluation must be analyzed in peripheral blood granulocytes and
	requires confirmation by repeat testing within 6 months window
	CR: Eradication of a pre-existing abnormality
	PR: $\geq 50\%$ decrease in allele burden (partial response applies only to patients with at least 20% mutant allele burden at baseline)
Cytogenetic/molecular relapse	Re-emergence of a pre-existing cytogenetic or molecular abnormality that is confirmed by repeat testing

EMH, extramedullary hematopoiesis (no evidence of EMH implies the absence of pathology-or imaging study-proven nonhepatosplenic EMH); LCM, left costal margin; UNL, upper normal limit.

\*Baseline and posttreatment bone marrow slides are to be interpreted at one sitting by a central review process. Cytogenetic and molecular responses are not required for CR assignment.

†Grading of MF is according to the European classification

Thiele et al. European consensus on grading bone marrow fibrosis and assessment of cellularity. *Haematologica*. 2005;90:1128.

It is underscored that the consensus definition of a CR bone marrow is to be used only in those patients in which all other criteria are met, including resolution of leukoerythroblastosis. It should also be noted that it was a particularly difficult task for the working group to reach a consensus regarding what represents a complete histologic remission.

‡Immature myeloid cells constitute blasts 1 promyelocytes 1 myelocytes 1 metamyelocytes 1 nucleated red blood cells. In splenectomized patients, <5% immature myeloid cells is allowed.

§See above for definitions of anemia response, spleen response, and progressive disease. Increase in severity of anemia constitutes the occurrence of new transfusion dependency or a  $\geq 20$  g/L decrease in hemoglobin level from pretreatment baseline that lasts for at least 12 weeks. Increase in severity of thrombocytopenia or neutropenia is defined as a 2-grade decline, from pretreatment baseline, in platelet count or absolute neutrophil count, according to the Common Terminology Criteria for Adverse Events (CTCAE) version 4.0. In addition, assignment to CI requires a minimum platelet count of  $\geq 25000 \times 10(9)/L$  and absolute neutrophil count of  $\geq 0.5 \times 10(9)/L$ .

||Applicable only to patients with baseline hemoglobin of  $<100$  g/L. In patients not meeting the strict criteria for transfusion dependency at the time of study enrollment (see as follows), but have received transfusions within the previous month, the pretransfusion hemoglobin level should be used as the baseline.

{Transfusion dependency before study enrollment is defined as transfusions of at least 6 units of packed red blood cells (PRBC), in the 12 weeks prior to study enrollment, for a hemoglobin level of  $<85$  g/L, in the absence of bleeding or treatment-induced anemia. In addition, the most recent transfusion episode must have occurred in the 28 days prior to study enrollment. Response in transfusion-dependent patients requires absence of any PRBC transfusions during any consecutive “rolling” 12-week interval during the treatment phase, capped by a hemoglobin level of  $\geq 85$  g/L.

#In splenectomized patients, palpable hepatomegaly is substituted with the same measurement strategy.

\*\*Spleen or liver responses must be confirmed by imaging studies where a  $\geq 35\%$  reduction in spleen volume, as assessed by MRI or CT, is required. Furthermore, a  $\geq 35\%$  volume reduction in the spleen or liver, by MRI or CT, constitutes a response regardless of what is reported with physical examination.

††Symptoms are evaluated by the MPN-SAF TSS. The MPN-SAF TSS is assessed by the patients themselves and this includes fatigue, concentration, early satiety, inactivity, night sweats, itching, bone pain, abdominal discomfort, weight loss, and fevers. Scoring is from 0 (absent/as good as it can be) to 10 (worst imaginable/as bad as it can be) for each item. The MPN-SAF TSS is the summation of all the individual scores (0-100 scale). Symptoms response requires  $\geq 50\%$  reduction in the MPN-SAF TSS.

‡‡Progressive disease assignment for splenomegaly requires confirmation my MRI or computed tomography showing a  $\geq 25\%$  increase in spleen volume from baseline.

Baseline values for both physical examination and imaging studies refer to pretreatment baseline and not to posttreatment measurements.

Source: Tefferi A, Cervantes, F, Mesa R, et al. Revised response criteria for Myelofibrosis: International Working Group-Myeloproliferative Neoplasms Research and treatment (IWG-MRT) and European LeukemiaNet (ELN) consensus report. *Blood*, 2013 122: 1395-1398

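### Two platelet floors in the response criteria are 1000 times too high by the protocol's own figures; read literally, no Phase 2 patient can be classed as clinical improvement

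*Combined protocol and SAP*

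**What the plan says.** Section 9.1 assigns one set of response criteria to Phase 1 and a revised set to Phase 2. The Phase 1 set is printed in Appendix I and the Phase 2 set in Appendix K.

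**Appendix K (Phase 2).** CI is an anemia, spleen or symptoms response without progression or worsening cytopenia. The footnote adds a condition on every such assignment: "assignment to CI requires a minimum platelet count of $\geq 25000 \times 10(9)/L", together with an "absolute neutrophil count of $\geq 0.5 \times 10(9)/L". In the same appendix, CR requires "Platelet count \geq 100 \times 10^9/L and" a value below the upper normal limit, and the lower PR tier starts at 50 x 10^9/L. Stable disease is "Belonging to none of the above listed response categories". Relapse includes "No longer meeting criteria for at least CI after achieving CR, PR, or CI".

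**Appendix I (Phase 1).** CI needs any one of four items. Item 3 asks for a doubling of the platelet count and an "absolute platelet count of at least 50,000 \times 10^9/L"; it is "applicable only for patients with baseline platelet count below 50 \times 10^9/L". Item 4, for neutrophils, asks for a doubling and "an ANC of at least 0.5 \times 10^9/L" when the baseline is below 1 x 10^9/L. The CR platelet floor is 100 x 10^9/L.

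**Elsewhere.** Inclusion criterion 8 (Section 4.1) admits patients with platelets of at least 25,000/µL and neutrophils above 1000/µL. Section 12.4 and the synopsis efficacy text count CR, PR and CI in the objective response rate. The synopsis statistics text counts complete and partial responses only.

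**The concern.** CI is the lowest response tier, yet its Phase 2 platelet floor lies far above the range that defines CR, which is itself capped at the upper normal limit. The Phase 1 floor cannot be squared with its own item, which otherwise asks only for a doubling from a low baseline. Both figures look like counts per µL that were given a 10^9/L unit.

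If the text is applied or programmed as printed, every would-be CI patient in Phase 2 becomes stable disease, and a patient who slips from CR or PR to CI level is called a relapse. Efficacy is part of the Phase 2 primary objective, and the objective response rate is the efficacy measure for which Section 12.4 specifies a confidence interval. If assessors silently correct the figure instead, a response category rests on a rule that is not written down.

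**Working it through.** **The plan's own figure.** The only sample-size figures are the Section 12.1 probabilities of at least one event or response in 20 patients. The formula 1 - (1 - p)^20 gives 64.2%, 87.8%, 96.1%, 98.8% and 99.9% for p = 5, 10, 15, 20 and 30%, in agreement with the printed table. They do not depend on the platelet floors.

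**Units.** 1 L = 10^6 µL, so 1 x 10^9/L = 1000/µL.

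| Figure | As printed | Per µL |
|---|---|---|
| Eligibility floor (Section 4.1) | 25,000/µL = 25 x 10^9/L | 25,000 |
| CR floor (Appendices I and K) | 100 x 10^9/L | 100,000 |
| Lower PR floor (Appendix K) | 50 x 10^9/L | 50,000 |
| CI floor (Appendix K) | 25000 x 10^9/L | 25,000,000 |
| CI item 3 baseline cut-off (Appendix I) | below 50 x 10^9/L | 50,000 |
| CI item 3 floor (Appendix I) | 50,000 x 10^9/L | 50,000,000 |

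**Ratios, Appendix K.**
- To the CR floor: 25000/100 = 250.
- To the lower PR floor: 25000/50 = 500.
- To the eligibility floor: 25000/25 = 1000.

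**Ratios, Appendix I item 3.**
- To the CR floor: 50,000/100 = 500.
- To its own baseline cut-off: 50,000/50 = 1000.
- Rise needed by an eligible patient with a baseline of 25 to just under 50 x 10^9/L: 50,000/50 = 1000-fold to 50,000/25 = 2000-fold, where the item otherwise asks for 2-fold.

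**Neighbouring items.** The neutrophil floor in the same Appendix K sentence is 0.5 x 10^9/L = 500/µL. In Appendix I item 4 the floor over the baseline cut-off is 0.5/1 = 0.5, against 1000 for platelets in item 3. Only the platelet figures are out of scale.

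**Dividing by 1000.** Appendix K gives 25 x 10^9/L, equal to the eligibility floor. Appendix I gives 50 x 10^9/L, equal to the item's own baseline cut-off and to a doubling from the eligibility floor (2 x 25 = 50).

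**Reach in each phase.** The Appendix K floor conditions every CI, so literal use leaves none. In Appendix I the four items are alternatives, so literal use closes item 3 only. Item 4 is already largely unavailable: it needs baseline neutrophils below 1 x 10^9/L, while entry requires more than 1000/µL, the same value. Only a fall between screening and baseline would open it. The hemoglobin/transfusion and spleen items are the main routes left.

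**Illustration (assumed counts; the documents give none).** Suppose that 6 of 20 evaluable Phase 2 patients would be CI at the intended floor and none CR or PR. Exact binomial 95% intervals:
- Intended floor: 6/20 = 30% (11.9 to 54.3).
- Literal floor: 0/20 = 0%; the upper limit is 1 - 0.025^(1/20) = 16.8%.

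**The case against.** The strongest reply is that nobody would apply a floor of 25 million/µL. Response assessment is scheduled as a visit procedure, the documents do not describe a programmed derivation, both appendices cite their published source, and a hematologist would probably read the figures as 25 and 50 x 10^9/L. This stands as a limit on the consequence. It does not make the printed rule right, and no other passage corrects it.

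The downstream reach is also modest:
- Section 12.4 plans no formal efficacy test.
- CR, PR, and the MRI spleen and symptom summaries do not use these floors.
- Under the synopsis statistics wording the rate would not move, although the CI row would still be empty.
- No separate relapse analysis is planned.
- The clinically active dose (Section 6.1.1) refers to response rate without a numeric threshold and is a judgment of the investigator/medical monitor and sponsor, so the link is indirect.

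A PDF-reading fault is an unlikely explanation: the two figures sit in separate appendices, are written differently (one with a comma), and are out by the same factor.

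A reader might infer that the Phase 1 response rate is biased downward. The documents do not support a net direction. CI item 1 in the same Appendix I list asks for a hemoglobin rise of only 2 g/L, where Appendix K asks for 20 g/L and Appendix I's own footnote uses 20 g/L for a decline. If that is also a scale error, it works in the lenient direction.

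**Conclusion.** Both platelet floors are wrong as written, by a factor of 1000 against the protocol's own eligibility floor (Appendix K) and baseline cut-off (Appendix I, item 3). Under literal use, Phase 2 CI is necessarily zero and the Section 12.4 response rate reduces to CR plus PR; in Phase 1 the platelet route is closed.

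The factor and the internal conflict rest only on figures in the documents. The effect on results rests on an assumption of literal use, which nothing in the documents shows. The fall from 30% to 0% also rests on assumed counts and on 20 evaluable patients, whereas Phase 2 enrols up to 20 and efficacy is analysed in the Efficacy Population. A reader might go further and infer that patients were in fact misclassified, or that the choice of dose was affected; the documents support neither. The point should be fixed because the figures define a response category and correcting them is nearly free.

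**What to change.** 1. After the sponsor confirms both values against the cited criteria, which were not available here, replace 25000 x 10(9)/L with 25 x 10^9/L in the Appendix K footnote and 50,000 x 10^9/L with 50 x 10^9/L in Appendix I, CI item 3. Derive response from the corrected values.
2. Re-check patients who were *not* assigned CI because of these floors. In Phase 1, these are patients with baseline platelets below 50 x 10^9/L whose count at least doubled and reached 50 x 10^9/L. In Phase 2, they are any patients who otherwise met CI. The duration requirements (8 weeks in Appendix I, 12 weeks in Appendix K) still apply. Reviewing only platelet-based CI calls already made would miss the patients at issue.
3. In the same pass, confirm the hemoglobin increment in Appendix I, CI item 1 (2 g/L against 20 g/L).
4. As a separate editorial correction, make Section 9.1 point to Appendix I for Phase 1 and Appendix K for Phase 2; it now names only Appendix I.

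The cost is two corrected figures, one confirmation, one cross-reference and a re-check of existing response data. No new data are needed.
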